3.2.4.1. Treatment-emergent Laboratory Abnormality and Toxicity

A treatment-emergent laboratory abnormality is defined as value outside the normal range which occurs on or after the start of IMP and up to 28 days following discontinuation of IMP.

A treatment-emergent laboratory toxicity is defined as an increase of at least one CTCAE toxicity grade (Version 5) from the baseline assessment at any post baseline visit which occurs after the first administration of IMP and through last test results of the study. If a laboratory assessment obtained on Day 1 with unknown collection times will be assumed to be an assessment prior to the initiation of IMP. If the relevant baseline assessments are missing for a given subject, then any post-baseline graded toxicity (i.e., at least Grade 1) is considered a treatment-emergent laboratory toxicity.

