5.15.5. Clinical Laboratory Assessments

Descriptive summaries of selected (quantitative) clinical laboratory results will be presented by treatment group and study visit. Laboratory values outside the normal range for each systematically collected hematology, blood chemistry, and urinalysis parameter will be identified. Each subject's hematology, blood chemistry, and quantitative urinalysis values will be flagged as "low" (below the lower limit of normal/LLN), "normal" (within the normal range), or "high" (above the upper limit of normal/ULN) relative to the normal ranges of the central laboratory. Each subject's qualitative urinalysis results will be flagged as "normal" or "abnormal." In addition, toxicity grade will be determined for laboratory tests with toxicity grade based on Common Terminology Criteria for Adverse Events (CTCAE) Version 5.0 with implementation specifications in [Section 9.8](#). The result of each laboratory test for individual

subjects will be presented in a listing with the normal range defined by the central laboratory, the status relative to the normal range, and the CTCAE toxicity grade.

Shift table will be used to summarize shifts from baseline toxicity grades to greatest (worst) treatment-emergent laboratory toxicity grades based on CTCAE criteria. For hematology and, blood chemistry, and quantitative urinalysis parameters that no CTCAE toxicity grade was defined, a shift table for each laboratory test will be based on the shift from baseline high/normal/low status to the status of the maximum post-baseline value and the minimum post-baseline value (including test results from unscheduled visits, if any). Similarly, for qualitative urinalysis parameters, shifts from baseline normal/abnormal status to the worst post-baseline status will be summarized.

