**Lab Test = Alkaline Phosphatase**

CTCAE Term	Grade 1	Grade 2	Grade 3	Grade 4	Grade 5
Alkaline phosphatase increased	>ULN - 2.5 x ULN if baseline was normal; 2.0 - 2.5 x baseline if baseline was abnormal	>2.5 - 5.0 x ULN if baseline was normal; >2.5 - 5.0 x baseline if baseline was abnormal	>5.0 - 20.0 x ULN if baseline was normal; >5.0 - 20.0 x baseline if baseline was abnormal	>20.0 x ULN if baseline was normal; >20.0 x baseline if baseline was abnormal	-

Alkaline Phosphatase will have grades 1-4 and grading is based ULN only.

- Grade 1 being any values from the ULN to 2.5 x ULN
- Grade 2 from >2.5 to 5.0 x ULN
- Grade 3 from >5.0 to 20.0 x ULN
- Grade 4 from >20.0 x ULN

Lab Test = Alanine Aminotransferase

CTCAE Term	Grade 1	Grade 2	Grade 3	Grade 4	Grade 5
Alanine aminotransferase increased	>ULN - 3.0 x ULN if baseline was normal; 1.5 - 3.0 x baseline if baseline was abnormal	>3.0 - 5.0 x ULN if baseline was normal; >3.0 - 5.0 x baseline if baseline was abnormal	>5.0 - 20.0 x ULN if baseline was normal; >5.0 - 20.0 x baseline if baseline was abnormal	>20.0 x ULN if baseline was normal; >20.0 x baseline if baseline was abnormal	-

ALT will have grades 1-4 and grading is based ULN only.

- Grade 1 being any values from the ULN to 3.0 x ULN
- Grade 2 from >3.0 to 5.0 x ULN
- Grade 3 from >5.0 to 20.0 x ULN
- Grade 4 from >20.0 x ULN

Lab Test = Aspartate Aminotransferase

CTCAE Term	Grade 1	Grade 2	Grade 3	Grade 4	Grade 5
Aspartate aminotransferase increased	>ULN - 3.0 x ULN if baseline was normal; 1.5 - 3.0 x baseline if baseline was abnormal	>3.0 - 5.0 x ULN if baseline was normal; >3.0 - 5.0 x baseline if baseline was abnormal	>5.0 - 20.0 x ULN if baseline was normal; >5.0 - 20.0 x baseline if baseline was abnormal	>20.0 x ULN if baseline was normal; >20.0 x baseline if baseline was abnormal	-

ALT will have grades 1-4 and grading is based ULN only.

- Grade 1 being any values from the ULN to 3.0 x ULN
- Grade 2 from >3.0 to 5.0 x ULN
- Grade 3 from >5.0 to 20.0 x ULN
- Grade 4 from >20.0 x ULN

Lab Test = Bilirubin

CTCAE Term	Grade 1	Grade 2	Grade 3	Grade 4	Grade 5
Blood bilirubin increased	>ULN - 1.5 x ULN if baseline was normal; > 1.0 - 1.5 x baseline if baseline was abnormal	>1.5 - 3.0 x ULN if baseline was normal; >1.5 - 3.0 x baseline if baseline was abnormal	>3.0 - 10.0 x ULN if baseline was normal; >3.0 - 10.0 x baseline if baseline was abnormal	>10.0 x ULN if baseline was normal; >10.0 x baseline if baseline was abnormal	-

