- Grade 3 from >6.0 to 7.0 mmol/L,
- Grade 4 from >7.0 mmol/L

Hypokalemia will have grades 1, 3, and 4,

- Grade 1 being any values from the LLN to 3.0 mmol/L,
- Grade 3 from >2.5 to 3.0 mmol/L,
- Grade 4 <2.5 mmol/L

Lab Test = Sodium

CTCAE Term	Grade 1	Grade 2	Grade 3	Grade 4	Grade 5
Hypernatremia	>ULN - 150 mmol/L	>150 - 155 mmol/L; intervention initiated	>155 - 160 mmol/L; hospitalization indicated	>160 mmol/L; life-threatening consequences	Death
Hyponatremia	<LLN - 130 mmol/L	125-129 mmol/L and asymptomatic	125-129 mmol/L symptomatic; 120-124 mmol/L regardless of symptoms	<120 mmol/L; life-threatening consequences	Death

Hypernatremia will have grades 1-4,

- Grade 1 being any values from the ULN to 150 mmol/L,
- Grade 2 from >150 to 155 mmol/L,
- Grade 3 from >155 to 160 mmol/L,
- Grade 4 from >160 mmol/L

Hyponatremia will have grades 1-4,

- Grade 1 being any values from the LLN to 130 mmol/L,
- Grade 2 from 125 to <130 mmol/L,
- Grade 3 from 120 to <125 mmol/L,
- Grade 4 <120 mmol/L

Lab Test = Triglycerides

CTCAE Term	Grade 1	Grade 2	Grade 3	Grade 4	Grade 5
Hypertriglyceridemia	150 mg/dL - 300 mg/dL; 1.71 mmol/L - 3.42 mmol/L	>300 mg/dL - 500 mg/dL; >3.42 mmol/L - 5.7 mmol/L	>500 mg/dL - 1000 mg/dL; >5.7 mmol/L - 11.4 mmol/L	>1000 mg/dL; >11.4 mmol/L; life-threatening consequences	Death

Triglycerides will have grades 1-4,

- Grade 1 being any values from the 150 to 300 mg/dL,
- Grade 2 from >300 to 500 mg/dL,
- Grade 3 from >500 to 1000 mg/dL,
- Grade 4 from >1000 mmol/L

Lab Test = Uric Acid

CTCAE Term	Grade 1	Grade 2	Grade 3	Grade 4	Grade 5
Hyperuricemia	>ULN without physiologic consequences	-	>ULN with physiologic consequences	Life-threatening consequences	Death

Uric Acid will not be CTCAE graded.

Lab Test = Bicarbonate or CO₂

CTCAE Term	Grade 1	Grade 2	Grade 3	Grade 4	Grade 5
Blood bicarbonate decreased	<LLN and no intervention initiated	-	-	-	-

Bicarbonate or CO₂ will not be CTCAE graded.

Lab Test = Phosphorus or Phosphate

CTCAE Term	Grade 1	Grade 2	Grade 3	Grade 4	Grade 5
Hypophosphatemia	Laboratory finding only and intervention not indicated	Oral replacement therapy indicated	Severe or medically significant but not immediately life-threatening; hospitalization or prolongation of existing hospitalization indicated	Life-threatening consequences	Death

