Hyperphosphatemia	Laboratory finding only and intervention not indicated	Noninvasive intervention indicated	Severe or medically significant but not immediately life-threatening; hospitalization or prolongation of existing hospitalization indicated	Life-threatening consequences; urgent intervention indicated (e.g., dialysis)	Death

Phosphorus or Phosphate will not be CTCAE graded.

Lab Test = Serum pH [This is not urine pH]

CTCAE Term	Grade 1	Grade 2	Grade 3	Grade 4	Grade 5
Acidosis	pH <normal, but >=7.3	-	pH <7.3	Life-threatening consequences	-
Alkalosis	pH >normal, but <=7.5	-	pH >7.5	Life-threatening consequences	-

Serum pH will be graded in both directions with Grades 1 and 3 only.

Acidosis Grade 1 .<LLN, but >=7.3 Grade 3, pH < 7.3

Alkaosis Grade 1 .>ULN, but <=7.5 Grade 3, pH < 7.5

Lab Test = Activated Partial Thromboplastin Time

CTCAE Term	Grade 1	Grade 2	Grade 3	Grade 4	Grade 5
Activated partial thromboplastin time prolonged	>ULN - 1.5 x ULN	>1.5 - 2.5 x ULN	>2.5 x ULN; bleeding	-	-

APTT will be graded in Grade 1-3

- Grade 1 being any values from the >ULN to 1.5 x ULN,
- Grade 2 from >1.5 to 2.5 x ULN,
- Grade 3 from >2.5 x ULN,

Lab Test = International Normalized Ratio

CTCAE Term	Grade 1	Grade 2	Grade 3	Grade 4	Grade 5
INR increased	>1.2 - 1.5; >1 - 1.5 x baseline if on anticoagulation; monitoring only indicated	>1.5 - 2.5; >1.5 - 2.5 x baseline if on anticoagulation; dose adjustment indicated	>2.5; >2.5 x baseline if on anticoagulation; bleeding	-	-

INR will be graded in Grade 1-3 without baseline factor

- Grade 1 being any values from the >1.2 to 1.5,
- Grade 2 from >1.5 to 2.5,
- Grade 3 from >2.5,

Lab Test = Eosinophils

CTCAE Term	Grade 1	Grade 2	Grade 3	Grade 4	Grade 5
Eosinophilia	>ULN and >Baseline	-	Steroids initiated	-	-

Eosinophils will not be CTCAE graded

Lab Test = Hemoglobin

CTCAE Term	Grade 1	Grade 2	Grade 3	Grade 4	Grade 5
Anemia	Hemoglobin (Hgb) <LLN - 10.0 g/dL; <LLN - 6.2 mmol/L; <LLN - 100 g/L	Hgb <10.0 - 8.0 g/dL; <6.2 - 4.9 mmol/L; <100 - 80g/L	Hgb <8.0 g/dL; <4.9 mmol/L; <80 g/L; transfusion indicated	Life-threatening consequences; urgent intervention indicated	Death
Hemoglobin Increased	Increase in > 0-2	Increase in >2-4g/dL	Increase > 4 g/DL	-	Death

Decreased Hemoglobin will have grades 1-3, with

- Grade 1 being any values from the LLN to 10 g/DL,
- Grade 2 from 8 to < 10 g/DL and
- Grade 3 < 8 g/DL

Increased Hemoglobin will not be graded.

Lab Test = CD4 Lymphocytes

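### SAP 9.8 starts Grade 1 at the LLN or ULN itself for 18 protocol-required laboratory tests, against the strict CTCAE rows printed above, so a normal value at the limit can be graded in two ways

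*SAP*

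**What the plan says.** SAP 9.8 handles each laboratory test in two layers: the CTCAE row, then bullets stating how it will be programmed. SAP 5.15.5 names 9.8 as the implementation specification for grading.

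For sodium, the CTCAE rows for Grade 1 are "<LLN - 130 mmol/L" (low) and ">ULN - 150 mmol/L" (high). The bullets beneath read "Grade 1 being any values from the LLN to 130 mmol/L" and "Grade 1 being any values from the ULN to 150 mmol/L". ALT and AST follow the same pattern: "Grade 1 being any values from the ULN to 3.0 x ULN". The APTT bullet, by contrast, keeps the sign: "Grade 1 being any values from the >ULN to 1.5 x ULN".

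Three other places in the SAP bear on a value equal to the limit:

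- **5.15.5** flags a result low only when it is below the LLN and high only when it is above the ULN. A value equal to either is therefore "within the normal range".
- **4.1.20** says how limits reported with symbols are used for grading and out-of-range status. A ULN given as ≤5 becomes 5, and one given as <5 becomes 4.99. The numeric ULN is thus the highest value still counted as normal.
- **3.2.4.1** defines treatment-emergent laboratory toxicity as "an increase of at least one CTCAE toxicity grade (Version 5) from the baseline assessment". If baseline is missing, any post-baseline grade of 1 or more counts.

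**The concern.** Read literally, the bullets put a value equal to the LLN or ULN into Grade 1. The CTCAE rows, 4.1.20 and 5.15.5 all treat that value as normal. A programmer working from the bullets and one working from the rows would write different code, and nothing in 9.8 says which prevails.

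Under the literal coding two things follow. A subject who moves from inside the range to exactly the limit gains a treatment-emergent toxicity. The listing, which under 5.15.5 shows both range status and grade, would then mark the same result as normal and as Grade 1. Conversely, a subject whose baseline sits exactly on the limit starts at Grade 1, so a later value truly outside the range but still Grade 1 is no increase and is not counted as emergent.

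**Working it through.** The plan states no figure to reproduce. The check is a comparison of rules, followed by an illustration of size.

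**1. How many rules are affected.** I took every Grade 1 rule in 9.8 tied to the LLN or ULN, counted high and low separately, and compared bullet with CTCAE row.

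| | Rules | Bullet starts at the limit, row strict |
|---|---|---|
| All limit-based Grade 1 rules in 9.8 | 30 | 25 |
| Of these, tests in protocol Table 11 | 22 | 22 |

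The 22 rules cover 18 tests: albumin, ALP, ALT, AST, bilirubin, calcium (both directions), cholesterol, CPK, creatinine, GGT, low glucose, magnesium (both), potassium (both), sodium (both), low hemoglobin, low lymphocytes, neutrophils and low WBC. The other 3 of the 25 are amylase, lipase and CD4 count, which are not in Table 11. The 5 rules that keep a strict bound are fibrinogen, serum pH low, serum pH high, APTT and eGFR/CrCl; none is in Table 11.

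**2. What the section's own notation implies.** The bullets mark an excluded bound with a sign: low-sodium Grade 2 runs from 125 to <130, and high-sodium Grade 2 from >150 to 155. By that notation an unsigned limit is included.

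**3. Effect on a grade.** The documents give no LLN for sodium, so 135 mmol/L is an assumption.

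| Sodium (mmol/L) | Grade from bullet | Grade from CTCAE row |
|---|---|---|
| 136 | 0 | 0 |
| 135 (= LLN) | 1 | 0 |
| 134 | 1 | 1 |
| 130 | 1 | 1 |
| 129 | 2 | 2 |

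With an LLN of 133 or 136 the pattern is the same: only the value exactly at the limit changes.

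**4. How often a value lands on the limit.** Assume a normal distribution, a reference range covering the central 95%, and a reporting unit of w standard deviations. Then

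p = Φ(−1.96 + w/2) − Φ(−1.96 − w/2)

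- w = 0.2: Φ(−1.86) − Φ(−2.06) = 0.0314 − 0.0197 = 0.0117
- w = 0.4: Φ(−1.76) − Φ(−2.16) = 0.0392 − 0.0154 = 0.0238
- w = 0.5: Φ(−1.71) − Φ(−2.21) = 0.04363 − 0.01355 = 0.0301

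So about 1.2% to 3.0% of single values fall on a given limit. At a finer unit, w = 0.05, p is 0.0029.

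**5. Per subject.** Protocol Table 2 schedules three post-baseline safety draws (Weeks 11, 22 and 27). If they were independent, the share of subjects with at least one value on the limit would be 1 − (1 − p)³ = 3.5%, 7.0% and 8.8% for w = 0.2, 0.4 and 0.5.

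That is not the treatment-emergent count, which needs a Grade 0 baseline and no post-baseline value truly beyond the limit (such a subject would be counted anyway). Draws within a subject are also correlated. A simulation under the same normal model, with an assumed within-subject correlation of 0.5 to 0.7, gives for w = 0.2 to 0.5:

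- newly counted as treatment-emergent: 2.0% to 5.9% of subjects per test and limit
- true shift masked by a baseline value on the limit: 0.3% to 0.8%

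At w = 0.05 the newly counted share is 0.5% to 0.6%.

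**The case against.** The best counter-argument is that the unsigned wording is only shorthand for the CTCAE row directly above it. The SAP bases grading on CTCAE Version 5.0. Several deliberate departures are announced, such as grading on the ULN only or using a WHO criterion for high glucose, and none is announced at the limit. The 4.1.20 convention works only if a value must exceed the ULN to be graded. The drafting is also loose elsewhere: the low-potassium bullets put 3.0 in both Grade 1 and Grade 3 and leave 2.5 ungraded. It is risky to read intent into a missing sign.

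Most of this stands as evidence of intent. The strict reading is probably what was meant, and a programmer who follows the row will grade correctly. But it does not correct the text. The bullets are the programming specification, they depart from the rows on purpose in other respects, and they use signs where a bound is excluded. The potassium slip shows that boundary errors do get into these bullets. SAP 9.5 requires results to be verified by independent programming, and two programmers could disagree here with no written rule to settle it.

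A reader might infer more: that normal values will be misgraded, or that the comparison between arms will be diluted or biased. The documents support neither. Two codings are possible, and one is correct. Laboratory data are summarized descriptively, the rule is the same in both arms, and nothing suggests that values on the limit would be more common in one arm.

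**Conclusion.** The point holds as an inconsistency within SAP 9.8 that permits a wrong Grade 1 coding for 18 protocol-required tests. It is not an established error in the results.

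Its reach is narrow. Efficacy, Grades 2 to 4, the high/normal/low flags and the liver tables based on multiples of the ULN do not change. The separate definition of treatment-emergent laboratory abnormality, which requires a value outside the normal range, also does not change.

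Every percentage above rests on assumed reporting units, a normal distribution and a 95% reference range, none of which the documents give. The 3.5% to 8.8% range also needs independent draws and overstates the treatment-emergent share. These figures show only that the effect could be visible for a coarsely reported test such as sodium in whole mmol/L, and that it would be small for finely reported ones. This is a minor point, worth correcting because correction is free.

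**What to change.** In SAP 9.8, write <LLN or >ULN as the start of Grade 1 in the affected bullets, matching the CTCAE rows and the APTT bullet. Alternatively, add one sentence at the head of 9.8 stating that a value equal to the LLN or ULN is Grade 0. The single sentence is safer, because it also covers amylase, lipase and CD4 and cannot miss a bullet. The low-potassium boundaries at 3.0 and 2.5 mmol/L could be aligned with their CTCAE row in the same edit.

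The cost is a wording correction and a check that the grading program uses strict inequalities. No new data, analyses or outputs are needed.

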**Lab Test = Neutrophils**

CTCAE Term	Grade 1	Grade 2	Grade 3	Grade 4	Grade 5
Neutrophil count decreased	<LLN - 1500/mm ³ ; <LLN - 1.5 x 10 ⁹ /L	<1500 - 1000/mm ³ ; <1.5 - 1.0 x 10 ⁹ /L	<1000 - 500/mm ³ ; <1.0 - 0.5 x 10 ⁹ /L	<500/mm ³ ; <0.5 x 10 ⁹ /L	-

Neutrophils will have grades 1-4, with

- Grade 1 being any values from the LLN to 1500/mm³,
- Grade 2 from 1000 to <1500/mm³ and
- Grade 3 from 500 to <1000/mm³ and
- Grade 4 <500/mm³

Lab Test = Platelets

CTCAE Term	Grade 1	Grade 2	Grade 3	Grade 4	Grade 5
Platelet count decreased	<LLN - 75,000/mm ³ ; <LLN - 75.0 x 10 ⁹ /L	<75,000 - 50,000/mm ³ ; <75.0 - 50.0 x 10 ⁹ /L	<50,000 - 25,000/mm ³ ; <50.0 - 25.0 x 10 ⁹ /L	<25,000/mm ³ ; <25.0 x 10 ⁹ /L	-

Platelet count will not be CTCAE graded

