**Lab Test = WBC**

CTCAE Term	Grade 1	Grade 2	Grade 3	Grade 4	Grade 5
White blood cell decreased	<LLN - 3000/mm3; <LLN - 3.0 x 10e9 /L	<3000 - 2000/mm3; <3.0 - 2.0 x 10e9 /L	<2000 - 1000/mm3; <2.0 - 1.0 x 10e9 /L	<1000/mm3; <1.0 x 10e9 /L	-
Leukocytosis	-	-	>100,000/mm3	Clinical manifestations of leucostasis; urgent intervention indicated	Death

Decreased WBC will have grades 1-4, with

- Grade 1 being any values from the LLN to 3000/mm3,
- Grade 2 from 2000 to <3,000/mm3 and
- Grade 3 from 1000 to <2,000/mm3 and
- Grade 4 <1000/mm3

High WBC will have grade 1, with

- Grade 1 >11,000/mm3 (<https://www.aafp.org/afp/2000/1101/p2053.html>),

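### SAP 9.8 leaves platelets ungraded and caps high WBC at Grade 1, against the CTCAE limits printed beside both rules, so the grade-based tables cannot show severe values as severe

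*SAP*

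**What the plan says.** SAP Section 5.15.5 sets the general rule: "toxicity grade will be determined for laboratory tests with toxicity grade based on Common Terminology Criteria for Adverse Events (CTCAE) Version 5.0", implemented through Section 9.8. The summary follows: "Shift table will be used to summarize shifts from baseline toxicity grades to greatest (worst) treatment-emergent laboratory toxicity grades based on CTCAE criteria". Hematology and chemistry "parameters that no CTCAE toxicity grade was defined" get a shift table on high/normal/low status instead.

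Section 9.8 prints the CTCAE row for each test, followed by the rule the SAP will use.

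- **Platelets.** The row has four grades, all defined by the count alone. Grade 3 is "<50,000 - 25,000/mm ³ ; <50.0 - 25.0 x 10 ⁹ /L" and Grade 4 is "<25,000/mm ³ ; <25.0 x 10 ⁹ /L". The rule is "Platelet count will not be CTCAE graded".
- **WBC.** The Leukocytosis row has no Grade 1 or 2, and gives Grade 3 above 100,000/mm3. The rule is "High WBC will have grade 1, with" the single line "Grade 1 >11,000/mm3" and a web reference.

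SAP Section 3.2.4.1 defines a treatment-emergent laboratory toxicity as a rise of at least one CTCAE grade from baseline or, where baseline is missing, any post-baseline grade of 1 or more. Protocol Table 11 (Appendix 2) lists both platelet count and WBC as required hematology.

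**The concern.** Section 5.15.5 promises grading for tests that have a CTCAE grade, and Section 9.8 withdraws it for platelets without explanation. The reason that would fit several other ungraded tests is not available here. Phosphate, uric acid, bicarbonate, eosinophils and urine blood have CTCAE criteria that rest at least partly on an intervention or a clinical consequence. The platelet row needs only the number.

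For high WBC, the rule adds a grade that the printed row lacks and removes the one numeric grade that it has. Mild leukocytosis then enters tables described as CTCAE-based, while an extreme value carries the same grade as a marginal one.

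At stake is how faithfully the grade-based laboratory safety tables show severity. No efficacy result depends on it.

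**Working it through.** The plan states no figure to reproduce, so the check applies each rule and its printed row to the same values.

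**Inputs.** Platelet and WBC rows and rules: SAP 9.8. Toxicity definition: SAP 3.2.4.1, which counts a subject if worst post-baseline grade minus baseline grade is at least 1. The documents give no platelet LLN, so I assume 100,000 to 150,000/mm3. Grades 2 to 4 do not depend on that choice.

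**Step 1. Platelets (per mm3).**

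| Value | Printed row | SAP rule |
|---|---|---|
| 140,000 (LLN 150,000) | Grade 1 | no grade; low |
| 74,000 | Grade 2 | no grade; low |
| 49,000 | Grade 3 | no grade; low |
| 24,000 | Grade 4 | no grade; low |
| 5,000 | Grade 4 | no grade; low |

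The results for 74,000, 49,000 and 24,000 are the same at an LLN of 100,000, 130,000 or 150,000. With no grade there is no grade difference, so the toxicity definition cannot be met by any platelet fall.

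**Step 2. High WBC (per mm3).**

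| Value | Printed row | SAP rule |
|---|---|---|
| 10,500 | none | none |
| 11,001 | none | Grade 1 |
| 50,000 | none | Grade 1 |
| 100,001 | Grade 3 | Grade 1 |
| 250,000 | Grade 3 | Grade 1 |

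**Step 3. Shift in WBC.**

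- 8,000 to 120,000. SAP rule: 1 − 0 = 1, so it counts, but as Grade 1. Printed row: 3 − 0 = 3, so it counts as Grade 3.
- 12,000 to 120,000. SAP rule: 1 − 1 = 0, so it does not count. Printed row: 3 − 0 = 3, so it counts as Grade 3.

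Because WBC does have grades under Section 9.8, the high/normal/low shift table for ungraded tests does not fill this gap.

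**The case against.** The strongest reply is that severe values are not lost, and that is correct. Section 5.15.5 lists every result with its normal range and its status against that range. Section 3.2.4.1 separately defines a treatment-emergent laboratory abnormality as any out-of-range value, which includes low platelets. Descriptive summaries give the minimum and maximum, though only for selected tests. Protocol Appendix 2 requires clinically significant abnormalities to be reported as adverse events. These carry an intensity (Table 15) and are tabulated by it (SAP 5.15.1). The gap therefore lies in the grade-based tables and the grade column of the listings only.

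Second, Section 9.8 is openly an adapted scheme. It prints the CTCAE row next to each departure, references a source for the 11,000/mm3 cut-off, uses a WHO cut-off for hyperglycemia, and leaves increased hemoglobin ungraded despite numeric limits. The lower WBC cut-off also picks up values that the printed row ignores. This makes the 11,000/mm3 line largely a labelling matter. It does not explain the lost Grade 3 or the platelet omission.

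Three stronger readings are tempting, and the documents do not support them.

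- *Platelets miss both shift tables.* A reader might infer this because CTCAE does define platelet grades, so the fallback wording would exclude them. In context the fallback most naturally covers tests for which Section 9.8 sets no grade. The literal reading would also strip bicarbonate and eosinophils, which have printed rows and are ungraded. Platelets should get the high/normal/low table.
- *Every high WBC is Grade 1.* Only values above 11,000/mm3 are. A value above a lower laboratory ULN but not above 11,000/mm3 gets no grade.
- *The main laboratory display is compromised.* The SAP does not rank its displays, and the grade shift table is one of several.

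**Conclusion.** The point holds as a minor one. Two rules in Section 9.8 depart from the limits printed beside them, and the platelet omission has no stated reason. In the CTCAE shift tables and under the toxicity definition, platelet falls of every severity go uncounted and are shown at best as low. WBC above 100,000/mm3 appears as Grade 1, or does not count when baseline was already above 11,000/mm3.

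The number of subjects affected is probably very small. The documents give no rate for such values, and Protocol Section 2.3 reports no notable laboratory differences between tavapadon and placebo in previous trials. The values remain visible elsewhere in the safety output, and efficacy is unaffected. The conclusion rests on the text of SAP 3.2.4.1, 5.15.5 and 9.8. The only outside assumption is the platelet LLN, which does not affect Grades 2 to 4.

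**What to change.** In SAP Section 9.8:

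1. Replace the platelet line with the printed limits: Grade 1 below LLN to 75, Grade 2 below 75 to 50, Grade 3 below 50 to 25, Grade 4 below 25 (all x10^9/L).
2. Add Grade 3 for WBC above 100,000/mm3.
3. Move WBC above 11,000/mm3 out of the CTCAE grades and report it as a flag labelled as a non-CTCAE criterion.

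If the sponsor prefers to keep platelets ungraded, the SAP should give the reason and name the shift table that will show them.

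The cost is a few specification lines and slightly more table output. No new data are needed. The change should be made before unblinding, so that no regrading is done after the results are known.
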